## 9.10. Other aspects

No other aspects.

## 10. PROTECTION OF HUMAN SUBJECTS

For this study, participants from 5 different EU states will process individual data as collected in national electronic health record databases. Due to the sensitive nature of this personal medical data, it is important to be fully aware of ethical and regulatory aspects and to strive to take all reasonable measures to ensure compliance with ethical and regulatory issues on privacy.

All of the databases used in this study are already used for pharmaco-epidemiological research and have a well-developed mechanism to ensure that European and local regulations dealing with ethical use of the data and adequate privacy control are adhered to.

In agreement with these regulations, rather than combining person level data and performing only a central analysis, local analyses will be run, which generate non-identifiable data with less information that will be pooled across databases.

The output files are stored in the central Remote Research Environment (RRE) of the Erasmus MC. These output files do not contain any data that allow identification of subjects included in the study. In fact, each record is completely anonymous and does not contain any identifier key. Starting from this, the RRE implements further security measures in order to ensure a high level of stored data protection, according with the article 34 of legislative decree 196/2003 and article 22 of Regulation (EC) 45/2001.

In addition, a scientific advisory committee consisting of 3 external experts has been constituted to guarantee scientific soundness of the study and also to follow-up on the progress and the appropriate conduct of the study. The members of the scientific advisory committee will be involved in review of the data and preparation of the reports (yearly and final).

Members of the scientific advisory committee are the following: [name], [name]. [name] and [name]. [name].

## **11. MANAGEMENT AND REPORTING OF ADVERSE EVENTS/ADVERSE REACTIONS**

According to the new guidelines for good pharmacovigilance practice (EMA/873138/2011) there is no requirement for expedited reporting of adverse drug reactions from studies with secondary use of data (such as electronic health care databases).

All the identified adverse events/reactions will be summarized in the final study report.

## **12. PLANS FOR DISSEMINATING AND COMMUNICATING STUDY RESULTS**

As the study progresses interim results will be reported in a yearly basis.

Dissemination activities to be undertaken will have mainly, although not exclusively, a scientific nature (articles in scientific journals, presentations at conferences, etc.).

In order to allow national competent authorities to review the results and interpretations to be published in advance, the marketing authorization holder will communicate to the Agency and the competent authorities of the Member States in which the product is authorized, the final manuscript of the article within two weeks after first acceptance for publication.

## 14. APPENDIX

### 14.1. List of stand-alone documents

Not applicable

## 14.2. ENCePP checklist for study protocols

EUROPEAN MEDICINES AGENCY  
SCIENCE MEDICINES HEALTH

Doc.Ref. EMEA/540136/2009  
ENCePP Checklist for Study Protocols (Revision 2, amended)

European Network of  
Centres for  
Pharmacoepidemiology

Adopted by the ENCePP Steering Group on 14/01/2013

The European Network of Centres for Pharmacoepidemiology and Pharmacovigilance (ENCePP) welcomes innovative designs and new methods of research. This Checklist has been developed by ENCePP to stimulate consideration of important principles when designing and writing a pharmacoepidemiological or pharmacovigilance study protocol. The Checklist is intended to promote the quality of such studies, not their uniformity. The user is also referred to the ENCePP Guide on Methodological Standards in Pharmacoepidemiology which reviews and gives direct electronic access to guidance for research in pharmacoepidemiology and pharmacovigilance.

For each question of the Checklist, the investigator should indicate whether or not it has been addressed in the study protocol. If the answer is “Yes”, the page number(s) of the protocol where this issue has been discussed should be specified. It is possible that some questions do not apply to a particular study (for example in the case of an innovative study design). In this case, the answer ‘N/A’ (Not Applicable) can be checked and the “Comments” field included for each section should be used to explain why. The “Comments” field can also be used to elaborate on a “No” answer.

This Checklist should be included as an Annex by marketing authorization holders when submitting the protocol of a non-interventional post-authorization safety study (PASS) to a regulatory authority (see the Guidance on the format and content of the protocol of non-interventional post-authorization safety studies). Note, the Checklist is a supporting document and does not replace the format of the protocol for PASS as recommended in the Guidance and Module VIII of the Good pharmacovigilance practices (GVP).

**Study title:**

European Program of Post-Authorization Safety Studies for Protelos®/Osseor® through EU-ADR Alliance

**Study reference number:**

TBC

Section 1: Milestones	Yes	No	N/A	Page Number(s)
1.1 Does the protocol specify timelines for				
1.1.1 Start of data collection 				14
1.1.2 End of data collection 				14
1.1.3 Study progress report(s)				14
1.1.4 Interim report(s)				14
1.1.5 Registration in the EU PAS register				14
1.1.6 Final report of study results				14

Comments:

--

Section 2: Research question	Yes	No	N/A	Page Number(s)
2.1 Does the formulation of the research question and objectives clearly explain:				
2.1.1 Why the study is conducted? (e.g. to address an important public health concern, a risk identified in the risk management plan, an emerging safety issue)				15-16
2.1.2 The objectives of the study?				16-17
2.1.3 The target population? (i.e. population or subgroup to whom the study results are intended to be generalised)				18
2.1.4 Which formal hypothesis(-es) is (are) to be tested?				
2.1.5 if applicable, that there is no a priori hypothesis?				

Comments:

--

Section 3: Study design	Yes	No	N/A	Page Number(s)
3.1 Is the study design described? (e.g. cohort, case-control, randomised controlled trial, new or alternative design)				18
3.2 Does the protocol specify the primary and secondary (if applicable) endpoint(s) to be investigated?				21-22
3.3 Does the protocol describe the measure(s) of effect? (e.g. relative risk, odds ratio, deaths per 1000 person-years, absolute risk, excess risk, incidence rate ratio, hazard ratio, number needed to harm (NNH) per year)				33-36

Comments:

--

 Date from which information on the first study is first recorded in the study dataset or, in the case of secondary use of data, the date from which data extraction starts.

 Date from which the analytical dataset is completely available.

Section 4: Source and study populations	Yes	No	N/A	Page Number(s)
4.1 Is the source population described?				18
4.2 Is the planned study population defined in terms of:				
4.2.1 Study time period?				18
4.2.2 Age and sex?				27
4.2.3 Country of origin?				24-27
4.2.4 Disease/indication?				
4.2.5 Co-morbidity?				23-24
4.2.6 Seasonality?				
4.3 Does the protocol define how the study population will be sampled from the source population? (e.g. event or inclusion/exclusion criteria)				18-19

Comments:

--

Section 5: Exposure definition and measurement	Yes	No	N/A	Page Number(s)
5.1 Does the protocol describe how exposure is defined and measured? (e.g. operational details for defining and categorising exposure)				22
5.2 Does the protocol discuss the validity of exposure measurement? (e.g. precision, accuracy, prospective ascertainment, exposure information recorded before the outcome occurred, use of validation sub-study)				
5.3 Is exposure classified according to time windows? (e.g. current user, former user, non-use)				22
5.4 Is exposure classified based on biological mechanism of action and taking into account the pharmacokinetics and pharmacodynamics of the drug?				
5.5 Does the protocol specify whether a dose-dependent or duration-dependent response is measured?				22

Comments:

--

Section 6: Endpoint definition and measurement	Yes	No	N/A	Page Number(s)
6.1 Does the protocol describe how the endpoints are defined and measured?				20
6.2 Does the protocol discuss the validity of endpoint measurement? (e.g. precision, accuracy, sensitivity, specificity, positive predictive value, prospective or retrospective ascertainment, use of validation sub-study)				20, 36

Comments:

--

Section 7: Confounders and effect modifiers	Yes	No	N/A	Page Number(s)
7.1 Does the protocol address known confounders? (e.g. collection of data on known confounders, methods of controlling for known confounders)				23-24

Section 7: Confounders and effect modifiers	Yes	No	N/A	Page Number(s)
7.2 Does the protocol address known effect modifiers? (e.g. collection of data on known effect modifiers, anticipated direction of effect)				

Comments:

--

Section 8: Data sources	Yes	No	N/A	Page Number(s)
8.1 Does the protocol describe the data source(s) used in the study for the ascertainment of:				
8.1.1 Exposure? (e.g. pharmacy dispensing, general practice prescribing, claims data, self-report, face-to-face interview, etc.)				24-27
8.1.2 Endpoints? (e.g. clinical records, laboratory markers or values, claims data, self-report, patient interview including scales and questionnaires, vital statistics, etc.)				24-27
8.1.3 Covariates?				24-27
8.2 Does the protocol describe the information available from the data source(s) on:				
8.2.1 Exposure? (e.g. date of dispensing, drug quantity, dose, number of days of supply prescription, daily dosage, prescriber)				24-27
8.2.2 Endpoints? (e.g. date of occurrence, multiple event, severity measures related to event)				24-27
8.2.3 Covariates? (e.g. age, sex, clinical and drug use history, co-morbidity, co-medications, life style, etc.)				24-27
8.3 Is a coding system described for:				
8.3.1 Diseases? (e.g. International Classification of Diseases (ICD)-10)				24-27
8.3.2 Endpoints? (e.g. Medical Dictionary for Regulatory Activities(MedDRA) for adverse events)				24-27
8.3.3 Exposure? (e.g. WHO Drug Dictionary, Anatomical Therapeutic Chemical (ATC) Classification System)				24-27
8.4 Is the linkage method between data sources described? (e.g. based on a unique identifier or other)				

Comments:

--

Section 9: Study size and power	Yes	No	N/A	Page Number(s)
9.1 Is sample size and/or statistical power calculated?				27-29

Comments:

--

Section 10: Analysis plan	Yes	No	N/A	Page Number(s)
10.1 Does the plan include measurement of excess risks?				35
10.2 Is the choice of statistical techniques described?				32-35
10.3 Are descriptive analyses included?				32
10.4 Are stratified analyses included?				32-35
10.5 Does the plan describe the methods for adjusting for confounding?				32-35

Section 10: Analysis plan	Yes	No	N/A	Page Number(s)
10.6 Does the plan describe methods addressing effect modification?				

Comments:

--

Section 11: Data management and quality control	Yes	No	N/A	Page Number(s)
11.1 Is information provided on the management of missing data?				32
11.2 Does the protocol provide information on data storage? (e.g. software and IT environment, database maintenance and anti-fraud protection, archiving)				29-32
11.3 Are methods of quality assurance described?				29-32
11.4 Does the protocol describe possible quality issues related to the data source(s)?				36
11.5 Is there a system in place for independent review of study results?				37

Comments:

--

Section 12: Limitations	Yes	No	N/A	Page Number(s)
12.1 Does the protocol discuss:				35
12.1.1 Selection biases?				36
12.1.2 Information biases? (e.g. anticipated direction and magnitude of such biases, validation sub-study, use of validation and external data, analytical methods)				36
12.2 Does the protocol discuss study feasibility? (e.g. sample size, anticipated exposure, duration of follow-up in a cohort study, patient recruitment)				
12.3 Does the protocol address other limitations?				36

Comments:

--

Section 13: Ethical issues	Yes	No	N/A	Page Number(s)
13.1 Have requirements of Ethics Committee/Institutional Review Board approval been described?				25-27
13.2 Has any outcome of an ethical review procedure been addressed?				
13.3 Have data protection requirements been described?				36-37

Comments:

--

Section 14: Amendments and deviations	Yes	No	N/A	Page Number(s)
14.1 Does the protocol include a section to document future amendments and deviations?				14

Comments:

--

Section 15: Plans for communication of study results	Yes	No	N/A	Page Number(s)
15.1 Are plans described for communicating study results (e.g. to regulatory authorities)?				37
15.2 Are plans described for disseminating study results externally, including publication?				37

[figure not shown]
Comments:

--

Name of the main author of the protocol: [name]

Date: 07th January 2015

Signature:

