## 6. MILESTONES

Milestone	Planned date
Protocol submission to EMA	by 30 June 2014
Protocol approval by EMA	March 2015 *
Contract signature for study roll-out phase	April 2015*
Registration in the EU PAS register	April 2015*
Start of data collection	April 2015*
Statistical Analysis Plan	May 2015
End of data collection	End of June 2015
PSUR Update 1	October 2015
Start of data collection (second wave)	April 2016
End of data collection (second wave)	End of June 2016
PSUR Update 2	October 2016
Start of data collection (third wave)	April 2017
End of data collection (third wave)	End of June 2017
PSUR Update 3	October 2017
Final report of study results	End of November 2017

*\*Delay will impact the subsequent dates*

Milestones have been planned to maximise the efficiency and availability of data retrieval from the different data sources. A summary of such information is provided here:

Data source (Country)	Periodicity of updates	Time of the year when updates are released	Data availability for each update
SIDIAP (Spain)	Yearly	April-May	End (December 31 st ) of previous calendar year
IPCI (NL)	Yearly (twice is possible)	April-May	Variable as GPs provide not all at same time
THIN (UK)	Three times per year	Irregular	Variable as GPs provide not all at same time
HSD (Italy)	Every 6 months	June and December	End of previous calendar year (in June); up to June in December.
AUH (Denmark)	Yearly	May	December 31st the previous year

Both national regulations and prescribing practices have changed throughout the participating databases in recent months. As a consequence, in Italy, where GPs in primary care are not allowed anymore to initiate or renew strontium ranelate treatment since December 2013, the number of incident strontium ranelate users in the assessment period is expected to be null or very low. This point will be assessed for the first PSUR update (October 2015) as part of the analyses of the utilization patterns at population level (see [section 9.7.2.1](#)).

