### 9.5.1. RMM effectiveness study

[figure not shown]
Based on published studies, the combined prevalence of MI, CVD and PAD before the DHPC published in May 2013 is assumed to be of 19.2% in female and 29.5% in male new users of SR (Abrahamsen, 2014).

A total of **320** male users of SR will suffice to estimate with a 95% confidence and an absolute precision of  $\pm 0.05$ , an unchanged prevalence of MI/CVD/PAD of 29.5%. Similarly, **239** female SR users would suffice to estimate with a 95% confidence and an absolute precision of  $\pm 0.05$ , an unchanged prevalence of MI/CVD/PAD of 19.2%.

Regarding the prevalence of new indication/restrictions of use (severe osteoporosis, and second line therapy), recent data suggest that the prevalence of these would range from 13.0% (Svanstrom, 2014) to 53.1% (Abrahamsen, 2014) for previous fragility fracture (severe osteoporosis), and from 40.4% (Svanstrom, 2014) to 47.9% (Abrahamsen, 2014) for the use of SR as a second line anti-osteoporosis treatment. Given this, 383 users of SR would suffice to estimate (with 95% confidence and 5% precision) an unchanged prevalence of 53.1% (most conservative scenario) for both indications. Lower numbers would be needed if this prevalence either increases or decreases (See Figure (9.5.1) 1).

A number of scenarios with different possible prevalence rates of MI/CVD/PAD, previous osteoporotic fracture, and use as a second line anti-osteoporosis therapy amongst SR users in subsequent years in the period before the publication of the DHPC in May 2013 (*reference*) and after the publication of the second DHPC from April 2014 onwards (*assessment* period) are presented in Figure (9.5.1) 1.

**Figure (9.5.1) 1 - Number of SR users required to estimate the prevalence of contraindications or new indication/restrictions with a 5% absolute precision**

[figure not shown]
For the interrupted time series analyses (see details below), sample size calculations are related to the estimation of the number of observations or time points at which data will be collected. According to the quality criteria of Ramsey et al, at least 10 pre- and 10 post-intervention data points would be needed to reach at least 80% power to detect a change (if the autocorrelation is  $>0.4$ ) (Ramsay, 2003). Our outcomes will be estimated at monthly intervals to ensure that  $>10$  data points are available for both the pre-defined *reference* and *assessment* analysis periods.

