#### ***Contra-indications***

Prevalence of each of the contraindications will be estimated on a patient level (new and prevalent users of SR) by age, sex, period and country. 95% Confidence Intervals will be estimated using a binomial distribution.

Interrupted time series analyses will be carried out to assess the impact of the RMM on these. Each contributing data source will be analyzed using an interrupted times series design (Kastner, 2011), using repeated measures before (up until May 2013) and after intervention (from April 2014 onwards), using a *transitional* lag time period (from June 2013 to March 2014, both included) to control for secular trends. Using this design, each database acts as its own control.

Using the interrupted times series approach, we estimate the trend in the prevalence rates in monthly intervals during the study period in the three analysis periods, and test for changes pre- and post- intervention, using the *transitional* period as a pre-specified lag time for the intervention to take effect on a) the overall (absolute rate) of outcome, and b) the slope of the trend in rates of outcome.

Segmented linear regression models will be used to estimate the monthly proportions of outcomes. Controlling for baseline level and trend, the models estimate changes in levels and trends of rates after the pre-defined interventions. The regression model includes terms to estimate the pre-existing level for each rate in the first months of the observation period (intercept), trend in the rate before the interventions were introduced, change in level of the rate during the transitional/lag time period, and change in trend after the intervention (Serumaga, 2011).

These analyses will be conducted separately for prevalent and incident SR users.

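### The monthly segmented regression lists no calendar-month term and the assessment series is never a whole number of years, so any annual cycle in an outcome would leak into the estimated effect, mainly at the first update

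*Protocol*

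**What the plan says.** Protocol section 9.7.2.2 (Contra-indications) states the model: "Segmented linear regression models will be used to estimate the monthly proportions of outcomes". The listed terms begin with level and prior trend ("The regression model includes terms to estimate the pre-existing level for each rate in the first months of the observation period (intercept") and end with "change in level of the rate during the transitional/lag time period, and change in trend after the intervention". No calendar-month or harmonic term appears, and the design is said to control for secular trends only. The same section makes the resulting coefficient and p-value the measure of effectiveness.

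The two segments are compared "using repeated measures before (up until May 2013) and after intervention (from April 2014 onwards", with June 2013 to March 2014 as lag. Section 9.5.1 adds: "Our outcomes will be estimated at monthly intervals", with the aim of having more than 10 points in each period.

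Section 6 gives the data cut-offs. For Aarhus it is "December 31st the previous year"; SIDIAP and the June release of HSD also stop at the end of the previous calendar year. IPCI and THIN cut-offs vary.

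In the ENCePP checklist (section 14.2), "4.2.6 Seasonality" is ticked N/A under the stem "4.2 Is the planned study population defined in terms of".

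**The concern.** A segmented regression without seasonal terms is protected against an annual cycle only if the cycle averages out within each segment. The reference segment holds seven to nine full years, so it nearly does so there. The assessment segment starts in April and, in three of the five databases, ends in December, so it always lacks part of one winter. Any annual swing is then partly absorbed by the level-change and trend-change coefficients, which are the quantities used to judge the measures. What remains of the swing goes into the residual and inflates the standard error.

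The outcome most open to this is uncontrolled hypertension, because its definition in section 9.3.2 rests on blood pressure readings from the 3 months before initiation.

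**Working it through.** **Inputs.** Reference series: January 2004 to May 2013 = 9×12 + 5 = 113 months; SIDIAP from January 2006 = 7×12 + 5 = 89 months (section 9.2.2). Assessment series from April 2014 with a December cut-off: 9, 21 and 33 months for the 2015, 2016 and 2017 extractions (section 6). Seasonal half-amplitude A: not given in the protocol; assumed range 0 to 3 percentage points, that is a winter-to-summer swing of 0 to 6 points.

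**Calendar balance.** January to March makes up 30 of 113 reference months (27%). In the assessment series it is 0 of 9 (0%), 3 of 21 (14%) and 6 of 33 (18%).

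**Bias.** Take y(t) = A·cos(2π(month − peak)/12) with no true effect. Fit intercept, trend, level change at April 2014 and trend change by least squares, leaving out the lag months. The fitted coefficients are then pure bias. For the series from 2004:

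| Bias per unit of A | First update (9 months) | Second (21) | Third (33) |
|---|---|---|---|
| Level, January peak | -0.88 | -0.37 | -0.25 |
| Level, peak on the January/February boundary | -0.64 | -0.28 | -0.19 |
| Level, March peak | +0.28 | +0.07 | +0.03 |
| Level, worst phase (absolute) | 1.22 | 0.48 | 0.30 |
| Trend per month, January peak | +0.145 | +0.022 | +0.008 |
| Trend per month, March peak | -0.145 | -0.022 | -0.008 |

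SIDIAP's 89-month reference gives nearly the same values (January/February boundary: -0.65, -0.29, -0.20). So does giving the lag months their own level term (worst phase 1.23, 0.50, 0.32).

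In points, for a January peak: A = 1, 2, 3 gives a spurious level change of -0.88, -1.77, -2.65 at the first update and -0.25, -0.49, -0.74 at the last.

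**Standard error and false rejection.** Binomial simulation with no true effect, January peak, prevalence 19.2% (the section 9.5.1 figure for women) and an assumed 300 users per database-month, as A goes from 0 to 3:
- First update: the model SE of the level change rises from 1.48 to 2.02 points, against a true SD of about 1.5. Rejection at a nominal 5% goes from 4% to 18%, driven by the bias.
- Last update: the model SE rises from 0.91 to 1.26 points, against a true SD of about 0.9. Rejection falls from 5% to 3%.

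With an assumed 50 users per month, rejection stays between 4% and 7% at every update.

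**With one sine/cosine pair added.** The simulated level bias is within 0.12 points of zero at every update, and rejection is about 4% to 6%. If there is no seasonality, the SE grows by the following factors (range over 113 and 89 reference months):
- First update: 1.030 to 1.037 (level) and 1.043 to 1.055 (trend).
- Last update: at most 1.004 (level) and 1.006 (trend).

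**The case against.** Section 9.7 gives only the main statistics and defers detail to an analysis plan that is not shown. The list in 9.7.2.2 is not called complete, and a seasonal term could be added there. That stands, and it is why the omission is not an error in itself. The terms of this primary-objective model are nevertheless written out, and none is seasonal.

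Most outcomes are poor candidates for a seasonal swing. Ischaemic, peripheral arterial, cerebrovascular and thromboembolic history use a one-year look-back; fracture and earlier treatment count at any time before; prescriber experience is an attribute of the physician. This also stands, and leaves uncontrolled hypertension as the clear case.

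Four stronger readings are tempting, and the documents do not support them:
- A reader might infer from the N/A tick that the protocol denies seasonality in its analysis. The item asks only whether the population is defined by season, so the answer is acceptable.
- A reader might infer that every assessment window is a single April-to-December block. That is true only of the first update in three databases. Later windows contain one and two winters, and IPCI and THIN have no fixed December end.
- A reader might infer that a winter-peaking contraindication always looks reduced. The sign depends on the peak: with a March peak the level bias is positive. A 3-month look-back could itself push a midwinter blood pressure peak towards March.
- A reader might infer widespread false claims of success. The SE error is conservative, and the 18% rejection needs the first update, A = 3 and 300 users per month. Section 9.5.2 expects only 500 to 1,000 new users a year over all databases after the 2013 communication, or about 42 to 83 a month.

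**Conclusion.** The point holds as a conditional weakness of the stated model. The listed terms cannot separate an annual cycle from the level and trend change, because an assessment series of 9, 21 or 33 months is never a whole number of years in SIDIAP, Aarhus and HSD. The level bias is at most about 1.2A at the first update and 0.3A at the last; its direction depends on the peak month, and it is zero if there is no seasonality. All sizes in points rest on an assumed A. The main exposure is the first PSUR update, whose 9 assessment points in those databases also fall short of the more than 10 that section 9.5.1 promises. By the final report the bias is small, and what is left is some loss of power from the inflated SE. This is worth changing because the remedy is nearly free, not because the final conclusion is shown to be wrong.

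**What to change.** In section 9.7.2.2, or in the analysis plan with a reference from there, add one annual sine/cosine pair to the segmented regressions: at least for uncontrolled hypertension, preferably for all outcomes. It can be estimated even at the first update, because the 89 to 113 reference months carry the seasonal information, and it removes the bias of an annual sinusoidal cycle whatever its peak month. The cost is one sentence and 2 degrees of freedom out of 98 (89 + 9) to 146 (113 + 33) monthly points. If there is no seasonality, the SE rises by at most about 4% (level) or 5% (trend) at the first update and by under 1% at the last. The checklist entry needs no change.
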